6.6.4 Other Treatments Allowed on Study

Surgery (outside of the mandated prostatectomy and pelvic lymph node dissection), androgen deprivation therapy and radiation therapy are not permitted prior to the time of prostatectomy and pelvic lymph node dissection. However, after prostatectomy, these modalities may be used as clinically indicated. Use of these modalities will be recorded in the data capture form.

7.0 Dose Delays/Modifications for Adverse Events

This section contains recommendations for the management of adverse events except hypertension and proteinuria which are discussed in subsequent sections. The following table is provided as a reference for guiding dose reductions. Notably, given the short course of therapy rendered in this study (28 days), dose reductions below 2 mg BID are not permitted.

DOSE MODIFICATION SCHEMA FOR AXITINIB- RELATED ADVERSE EVENTS			
Dose Level	Dose	Dispensed as	
0 (Starting dose)	5 mg bid	1 x 5 mg tablet bid	
-1	3 mg bid		3 x 1 mg tablet bid
-2	2 mg bid		2 x 1 mg tablet bid

Patients developing an axitinib-related CTCAE Grade 1 or 2 adverse events may have their dose continued at the same dose level.

Patients removed from treatment for intolerable toxicity should still be followed with regular tumor assessments until disease progression or start of new treatment, and for survival thereafter.

The criterion for dose modification for study-drug-related adverse events (from previously on-going trials across the axitinib development program) is summarized in the table below:

CRITERIA FOR DOSE MODIFICATION FOR AXITINIB- RELATED ADVERSE EVENTS OTHER THAN HYPERTENSION	
Related Adverse Events	INTERVENTION
Grade 1	Continue at same dose level
Grade 2	Continue at same dose level
Grade 3 nonhematologic treatment-related toxicity*	Decrease dose to one lower dose level.
Grade 4 nonhematologic treatment-related toxicity or Grade 4 hematologic toxicity**	Interrupt dosing; re-start at one lower dose level as soon as improvement to CTCAE Grade ≤ 2 . Dose reductions below 2 mg BID are not permitted.

* Patients who develop Grade 3 nonhematologic toxicities that are controlled with symptomatic medications or Grade 3 asymptomatic biochemistry laboratory abnormalities may be continued at the same dose level at the discretion of the investigator.

** Patients who develop Grade 4 lymphopenia or Grade 4 asymptomatic biochemistry laboratory abnormality may continue study treatment without interruption.

Guidelines for dose reductions for specific adverse events are provided in the following sections.

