3.0 Patient Eligibility

3.1 Inclusion Criteria

3.1.1 Histologically confirmed diagnosis of prostate cancer

- 3.1.2 High-risk prostate cancer as defined by 1 of the 3 following criteria: (1) baseline PSA > 20, (2) clinical stage \geq T3a, and (3) Gleason score 8-9.
- 3.1.3 Subjects must be appropriate candidates for prostatectomy and pelvic lymph node dissection, as deemed by a multidisciplinary team. Subjects must provide informed consent to these procedures prior to initiating study treatment
- 3.1.4 Subjects must provide written informed consent prior to performance of study-specific procedures or assessments, and must be willing to comply with treatment and follow-up. Procedures conducted as part of the subject's routine clinical management (e.g., blood count, imaging study) and obtained prior to signing of informed consent may be utilized for screening or baseline purposes provided these procedures are conducted as specified in the protocol.
- 3.1.5 Adequate organ function as defined by the following criteria:
 - 3.1.5.1 absolute neutrophil count (ANC) \geq 1500 cells/mm³;
 - 3.1.5.2 platelets \geq 100,000 cells/mm³.
 - 3.1.5.3 Hemoglobin \geq 9.0 g/dL.
 - 3.1.5.4 AST and ALT \leq 2.5 x upper limit of normal (ULN);
 - 3.1.5.5 Total bilirubin \leq 1.5 x ULN;
 - 3.1.5.6 Serum creatinine \leq 1.5 x ULN or calculated creatinine clearance \geq 60 mL/min;
 - 3.1.5.7 Urinary protein <2+ by urine analysis (UA). If UA is \geq 2+ for protein then a 24-hour urine collection can be done and the patient may enter only if urinary protein is <2 g per 24 hours.
- 3.1.6 Male patients, age \geq 18 years.
- 3.1.7 ECOG performance status of 0 or 1.
- 3.1.8 Life expectancy of \geq 12 weeks.
- 3.1.9 No prior systemic therapy for prostate cancer
- 3.1.10 No evidence of preexisting uncontrolled hypertension as documented by 2 consecutive blood pressure readings taken within 1 hour. The baseline systolic blood pressure readings must be \leq 140 mm Hg, and the baseline diastolic blood pressure readings must be \leq 90 mm Hg. Patients whose hypertension is controlled by antihypertensive therapies are eligible.

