6.2 Laboratory Studies

A local laboratory is to be used to perform all clinical laboratory assessments. Laboratory tests should be performed as indicated in the Time and Events Table(s). All laboratories prior to week 9 may be performed/collected within +/- 3 days of the dates specified in the study calendar. From week 9 onwards, all laboratories may be performed/collected within +/- 7 days of the dates specified in the study calendar. Assessments may be performed more frequently if clinically indicated.

All laboratory tests with values that become clinically abnormal while the subject is participating in the study or within 28 days after the last dose of study drug should be repeated until the values return to normal or baseline.

Results for all unscheduled clinical laboratory assessments (i.e., haematology, TSH/T₄, coagulation parameters) should be recorded on an unscheduled laboratory form in the eCRF.

Hematology and Clinical Chemistry

Hematology and clinical chemistry laboratory parameters that should be reported include white blood cell count, hemoglobin, hematocrit, platelet count, sodium, potassium, chloride, carbon dioxide, BUN, creatinine, and blood glucose. Assays for hematology and clinical chemistry should be performed according to the study calendar. Estimated creatinine clearance should be calculated using the Cockcroft and Gault method.

Liver Function Tests

When a separate liver function test (LFT) panel is conducted, this panel should include the following: ALT, AST, alkaline phosphatase, and total bilirubin. A direct bilirubin level should be obtained if the total bilirubin level is greater than 1.5 x upper limit of normal (ULN). Liver chemistry threshold stopping criteria and dose modification guidelines have been designed to ensure subject safety.

Evaluation of Proteinuria To be eligible for the current protocol, urinary protein must be <2+ by standard urine analysis (UA). If UA is $\geq 2+$ for protein then a 24-hour urine collection can be done and the patient may enter only if urinary protein is <2 g per 24 hours. Proteinuria will be evaluated using the urine protein to creatinine ratio (UPC; see Appendix B). .

Coagulation Tests

Coagulation tests should be performed as specified in the Time and Events Table and also in response to an AE/SAE as clinically indicated. Coagulation tests include activated partial thromboplastin time (aPTT), prothrombin time (PT) and international normalized ratio (INR).

Lipid Tests

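### Footnote ** in section 7.0 allows axitinib to continue through any asymptomatic Grade 4 biochemistry value, with no exception for bilirubin, creatinine, ALT or AST

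*Combined protocol and SAP*

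**What the plan says.** The criteria table in section 7.0 gives a default for Grade 4 treatment-related nonhematologic toxicity: "Interrupt dosing; re-start at one lower dose level as soon as improvement to CTCAE Grade" 2 or lower. Footnote ** is attached to that row and reads: "Patients who develop Grade 4 lymphopenia or Grade 4 asymptomatic biochemistry laboratory abnormality may continue study treatment without interruption".

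Other text bears on how the footnote is read:

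- **Status of the section.** It opens with "This section contains recommendations for the management of adverse events". It describes the table as summarizing criteria from earlier axitinib trials.
- **Grade 3.** The default is a one-level reduction, but patients with "Grade 3 asymptomatic biochemistry laboratory abnormalities may be continued at the same dose level at the discretion of the investigator" (footnote *).
- **Event-specific rules.** Section 7.0 closes with "Guidelines for dose reductions for specific adverse events are provided in the following sections". The sections that follow are 7.1 (hypertension) and 7.2 (surgery).
- **Liver tests.** Section 6.2 and the synopsis both say: "Liver chemistry threshold stopping criteria and dose modification guidelines have been designed to ensure subject safety". Neither gives a threshold, an action or a location.
- **Entry limits.** Section 3.1.5 requires "Adequate organ function as defined by the following criteria", which include AST and ALT at most 2.5 x ULN, bilirubin at most 1.5 x ULN, and creatinine at most 1.5 x ULN or clearance of at least 60 mL/min.

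**The concern.** The footnote switches off the table's main protection for a whole class of laboratory findings. That class includes the tests that signal liver or kidney injury, which can be severe before symptoms appear. The same tests must be near normal at entry. The protocol also reports (section 2.10) roughly doubled axitinib exposure in moderate hepatic impairment. An isolated laboratory value is not the same as that condition, but it is a reason to treat liver values differently from other chemistries.

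The population raises the stakes. These men have no evidence of metastatic disease (3.2.2), and dosing is planned to end only 48 hours before prostatectomy (6.1.1). As written, the dose guidance points toward continuing when such a value is found, and holding the drug depends on individual judgment.

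**Working it through.** The plan states no figure on this point, so the check has two parts: whether anything else in the text sets a hold, and how often the footnote could apply.

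**1. Does another provision set a liver or renal hold for one patient?**

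| Provision | What it does | Sets a hold? |
|---|---|---|
| 7.1, 7.2 | Hypertension; surgery | No |
| 6.2, repeat testing | Abnormal tests "should be repeated until the values return to normal or baseline" | No, monitoring only |
| 6.2, direct bilirubin | Extra test if total bilirubin exceeds 1.5 x ULN | No, testing only |
| 6.2 and synopsis, liver criteria | Says that criteria have been designed | Not in the text available |
| 6.5 | Ends treatment for unacceptable adverse events or on investigator judgment | Possible, but no analyte or threshold is named |
| 13.4, Table 1 | Serious Grade 3-4 events to the DSMC in 5 calendar days | No, reporting only |
| 14.1.2 | Holds accrual | No, study level only |

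No creatinine dosing rule appears anywhere.

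**2. How often could it arise?**

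Inputs from section 8.1.7, Table 2 (single-agent axitinib):

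- Grade 4 total bilirubin: 2/347 = 0.58% (stated 0.6%).
- Grade 4 creatinine: 4/347 = 1.15% (stated 1.2%).
- Grade 4 SGOT (AST): 0/347. Grade 4 SGPT (ALT): 0/345.

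Arm sizes from 14.1.1: 22 (powered) and 30 (recruited).

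Expected patients with Grade 4 bilirubin or creatinine = n x k / 347. Table 2 does not show overlap, so k = 4 if both bilirubin cases were also creatinine cases, and k = 6 if no patient had both.

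- n = 22: 22 x 4/347 = 0.25 to 22 x 6/347 = 0.38.
- n = 30: 30 x 4/347 = 0.35 to 30 x 6/347 = 0.52.

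With k = 6, the binomial chance of at least one such patient is 32% for 22 treated and 41% for 30.

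**3. When would it matter?**

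The synopsis places chemistry and hepatic tests at baseline and weeks 2, 4 and 8. Dosing lasts 28 days, so the week-4 draw comes as dosing ends. Apart from unscheduled tests, the footnote matters mainly at week 2, when 28 - 14 = 14 dosing days remain (11 to 17 with the 3-day window).

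**4. What would a hold do to the course?**

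A 7-day interruption leaves (28 - 7)/28 = 21/28 = 75% of planned treatment, which just meets the minimum in 6.5. A delay of more than one week means removal under 6.5, and less than 75% of treatment means replacement.

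**The case against.** The case for leaving the footnote alone has real weight.

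- **Provenance.** The rule has a stated source in the axitinib program, and nothing in the documents shows that it caused harm. This stands: the footnote should not be described as an oversight.
- **Permissive wording.** It says treatment may continue, inside a section of recommendations, and 6.5 separately ends treatment for unacceptable adverse events. This also stands. It makes the missing discretion wording, compared with footnote *, a minor point.
- **Oversight.** Serious Grade 3-4 events reach the DSMC in 5 days whatever their attribution, so review is not limited to quarterly reports. That is correct, but an asymptomatic laboratory value is not automatically serious, and a report does not hold a dose.
- **Liver criteria.** They may exist outside the text available; several appendices that the protocol cites are not in it. No appendix is cited for liver dosing rules, however, and the statement about liver criteria would not cover creatinine.
- **Rarity.** Grade 4 ALT or AST was never observed, and the exposure window is short. This limits the size of the point but does not remove it.

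A reader might infer that the protocol requires dosing through liver or renal injury, that no liver stopping criteria exist, or that patients are otherwise unprotected. The documents support none of these. The footnote permits and does not require, the liver criteria are stated to exist, and the investigator can stop the drug at any time.

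**Conclusion.** The point holds in a limited form. Footnote ** is a stated permission that overrides the table's own Grade 4 interruption for liver and renal chemistry, and no provision in the text available restores a specific hold for an individual patient. It is a low-frequency safety weakness that is worth correcting because correction is cheap.

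The 0.25 to 0.52 expected patients assume that Table 2's rates apply here. The number the footnote governs is probably smaller. Those rates carry no attribution to drug and do not say which cases were asymptomatic. This trial doses for only 28 days and requires near-normal values at entry. The creatinine rate is itself uncertain: Table 2 shows no Grade 3 cases but 4 Grade 4 cases, without explanation. For ALT and AST no projection is made; including them rests on clinical logic and not on observed events.

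**What to change.** Amend footnote ** so that treatment-related Grade 4 bilirubin, creatinine, ALT and AST are excluded from it and follow the table's existing default: interrupt, then restart one level lower once the value is Grade 2 or lower. No new test or threshold is needed.

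Two further clarifications are optional: put continuation for other Grade 4 chemistries at the investigator's discretion, as footnote * does for Grade 3; and have the liver sentence in 6.2 and the synopsis say where the governing criteria are and that they override footnote **. Any numeric thresholds are for the clinical team.

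The cost is a rare extra interruption: at Table 2's rates, at most about 0.4 expected in 22 axitinib patients or 0.5 in 30. A hold of up to 7 days causes neither removal nor replacement by itself. The documents do not show that recovery from Grade 4 to Grade 2 takes a week or less, so some holds may end treatment. If every one did, the same 0.4 to 0.5 would be the ceiling on added replacements.

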7.1 Axitinib Dose Reduction for Hypertension

In sponsored studies, patients treated with axitinib were issued blood pressure cuffs for home monitoring and instructed to measure their blood pressure (BP) twice daily, prior to taking each dose. All blood pressure measurements were recorded in a diary and brought to the nurse or study coordinator at each clinic visit. Patients were instructed by the study staff to contact their physician immediately for guidance if their systolic blood pressure rises above 150 mm Hg, diastolic blood pressure rises above 100 mm Hg, or if they develop symptoms perceived to be related to elevated BP (eg, headache, visual disturbance). See below for dose modifications for hypertension.

New or additional antihypertensive therapy (See Section 6.6.3, Concomitant Medication(s) for guidance) should be started if 2 BP readings, preferably taken in the clinic and separated by at least 1 hour, show the following: 2 systolic BP readings greater than 150 or 2 dBP readings greater than 100 mm Hg. Alternately, the dose of existing antihypertensive medication(s) may be increased. If the patient is already on maximal antihypertensive treatment, the axitinib dose should be reduced by 1 dose level.

Patients who have 2 systolic BP readings, separated by at least 1 hour, greater than 160 mm Hg, or 2 dBP readings, separated by at least 1 hour, greater than 105 mm Hg, should have treatment with axitinib held. (Note: if axitinib is held, patients receiving antihypertensive medications should monitor closely for hypotension and restart axitinib at one lower dose level as soon as BP is $<150/100$ mm Hg. Plasma half-life of axitinib is 2 – 4 hours and BP usually decreases within 1-2 days following dose interruption.) Treatment with axitinib should be restarted at 1 lower dose level as soon as the systolic blood pressure reduces to less than 150 mm Hg and the dBP reduces to less than 100 mm Hg.

Patients who develop recurrent systolic hypertension (2 BP readings separated by at least 1 hour show systolic pressure >150 mm Hg) or recurrent diastolic BP >100 mm Hg following previous axitinib dose reduction should undergo another dose reduction by one dose level.

Patients removed from treatment for intolerable toxicity should still be followed with regular tumor assessments until disease progression or start of new treatment, and for survival thereafter. Guidance on dose interruption and reduction for hypertension is summarized in the table below.

HYPERTENSION MANAGEMENT PLAN FOR AXITINIB			
Degree of Blood Pressure Elevation		Management	
Systolic Pressure 2 BP readings separated by at least 1 hour show systolic pressure >150 mm Hg	OR	Diastolic Pressure 2 BP readings separated by at least 1 hour show diastolic pressure >100 mm Hg	If not on maximal antihypertensive treatment, institute new or additional antihypertensive medication and maintain dose of axitinib.
2 BP readings separated by at least 1 hour show systolic pressure >160 mm Hg		2 BP readings separated by at least 1 hour show diastolic pressure >105 mm Hg	If on maximal antihypertensive treatment, reduce axitinib to one lower dose level.
Recurrent hypertension following previous dose reduction (2 BP readings separated by at least 1 hour show systolic pressure >150 mm Hg)	OR	Recurrent dBP >100 mm Hg (2 BP readings separated by at least 1 hour) following previous dose reduction	Interrupt dosing*; adjust antihypertensive medication; as soon as BP is less than 150/100 mm Hg, restart axitinib at one lower dose level.

* If axitinib is held, patients receiving antihypertensive medications should monitor closely for hypotension. Plasma half-life of axitinib is 2 – 4 hours and BP usually decreases within 1-2 days following dose interruption.

7.2 Axitinib Dose Interruption for Surgery or Surgical Procedures

If a major surgery or an interventional procedure (eg, endoscopy) is required, treatment with axitinib must be interrupted at least 24 hours before the procedure and the patient blood pressure should be monitored closely for hypotension. Patients may resume axitinib seven days after minor surgery and 2-3 weeks after major surgery, assuming wound has completely healed and no wound healing complications (eg, delayed healing, wound infection or fistula).

[figure not shown]
8.0 Agent Information

8.1 Axitinib (AG013736)

NSC#:

8.1.1 Structure and Molecular Weight:

C22H18N4OS (MW 386.47)

8.1.2 Supplier

Pfizer Oncology

8.1.3 Formulation

Axitinib is supplied as a series of aqueous film-coated tablets containing 5 mg or 1 mg of the freebase. Refer to the axitinib IB for information regarding the physical and chemical properties of axitinib and a list of excipients.

8.1.4 Storage

The intact bottles should be stored at controlled room temperature [20°C-25°C (68°F-77°F)]. Excursions are permitted between 15°C and 30°C.

8.1.5 Stability

Stability studies are ongoing.

8.1.6 Administration

Axitinib should be taken orally without food at least one hour before or two hours after a meal. The tablets should be swallowed whole and must not be crushed or broken. The time of day the tablets are taken should be relatively constant. If a dose is missed, the subject should take the dose as soon as possible, but not if there are less than 12 hours before the next dose is due. If the next dose is due in less than 12 hours, the subject should skip the missed dose and take the next dose as scheduled.

If vomiting occurs after taking axitinib another dose is not permitted on that day. The subject should resume taking axitinib at the next scheduled dose. If vomiting persists, the subject should be instructed to notify the investigator.

8.1.7 Human Toxicities

Table 1 summarizes the treatment-emergent adverse events in ($\geq 10\%$) cancer subjects who received single-agent axitinib regardless of whether the event was reported as related to axitinib treatment or other cause. The combined results are summarized for the following studies: Phase 1 studies in subjects with various solid tumors (Protocols A4061022 and A4061044), thyroid cancer (Protocols A4061014 and A4061027), melanoma (Protocol A4061015), NSCLC (Protocol A4061011), and RCC (Protocols A4061012, A4061023 and A4061035). Study A4061032 has not been included since it is an ongoing Phase 3 study. Study A4061013 was excluded since it involved subjects with hematological malignancies and the first-in-human (FIH) Phase 1 study A4060010 was excluded since a number of patients received starting doses above the recommended starting dose of 5 mg BID. Overall, the adverse events reported in

axitinib clinical studies are considered manageable, generally reversible and expected for this class of agents. For single-agent axitinib, the most common adverse events reported from 364 cancer subjects regardless of causality included fatigue (227 subjects, 62.4%), diarrhea (197 subjects, 54.1%), hypertension (173 subjects, 47.5%), anorexia (150 subjects, 41.2%), nausea (139 subjects, 38.2%), dysphonia (129 subjects, 35.4%), headache (104 subjects, 28.6%), palmar-plantar erythrodysaesthesia syndrome (104 subjects, 28.6%), weight decreased (100 subjects, 27.5%), cough (89 subjects, 24.5%), dyspnoea (88 subjects, 24.2%), constipation (86 subjects, 23.6%), arthralgia (83 subjects, 22.8%), vomiting (77 subjects, 21.2%), stomatitis (76 subjects 20.9%), and pain in extremity (73 subjects, 20.1%). Additionally, proteinuria was reported as an adverse event in 72 subjects (19.8%). Grade 3+ events occurred most frequently for hypertension (68 subjects, 18.7%) and fatigue (52 subjects, 14.3%).

Table 1. Treatment-Emergent, All-Causality Adverse Events Summarized by Descending Frequency Occurring in at Least 10% of Subjects with Solid Tumors Receiving Single Agent AG 013736*

MedDRA Preferred Term	Solid Tumor Single-Agent (N =364)		Grade 3+ n (%)
	All Grades n (%)		
Fatigue	227	(62.4)	52 (14.3)
Diarrhea	197	(54.1)	27 (7.4)
Hypertension	173	(47.5)	68 (18.7)
Anorexia	150	(41.2)	11 (3.0)
Nausea	139	(38.2)	6 (1.6)
Dysphonia	129	(35.4)	0 (0.0)
Headache	104	(28.6)	8 (2.2)
Palmar-plantar erythrodysaesthesia syndrome	104	(28.6)	25 (6.9)
Weight decreased	100	(27.5)	12 (3.3)
Cough	89	(24.5)	5 (1.4)
Dyspnoea	88	(24.2)	30 (8.2)
Constipation	86	(23.6)	2 (0.5)
Arthralgia	83	(22.8)	9 (2.5)
Vomiting	77	(21.2)	6 (1.6)
Stomatitis	76	(20.9)	7 (1.9)
Pain in extremity	73	(20.1)	11 (3.0)
Proteinuria	72	(19.8)	15 (4.1)
Dyspepsia	62	(17.0)	1 (0.3)
Mucosal inflammation	62	(17.0)	2 (0.5)
Abdominal pain	59	(16.2)	15 (4.1)
Rash	58	(15.9)	1 (0.3)
Back pain	57	(15.7)	6 (1.6)
Dizziness	49	(13.5)	1 (0.3)
Dry skin	49	(13.5)	1 (0.3)
Epistaxis	48	(13.2)	0 (0.0)

Insomnia	48	(13.2)	0	(0.0)
Oedema peripheral	47	(12.9)	0	(0.0)
Pyrexia	47	(12.9)	0	(0.0)
Dysgeusia	46	(12.6)	0	(0.0)
Oropharyngeal pain	41	(11.3)	0	(0.0)
Chest pain	40	(11.0)	5	(1.4)
Hypothyroidism	40	(11.0)	0	(0.0)
Dry mouth	38	(10.4)	0	(0.0)
Myalgia	38	(10.4)	4	(1.1)
Abdominal pain upper	37	(10.2)	4	(1.1)
Nasopharyngitis	37	(10.2)	0	(0.0)

Data in table represents combined safety data from individual studies including protocols A4061011, A4061012, A4061014, A4061015, A4061022, A4061023, A4061027, A4061035, and A4061044

Laboratory test results, summarized by maximum grade for subjects with solid tumors who received single-agent axitinib are presented in Table 2. Grade 3 hyponatremia was reported in 16 subjects (4.6%), elevations in SGOT in 11 subjects (3.2%), hyperglycemia in 13 subjects (3.8%) and proteinuria in 11 subjects (3.3%). Grade 4 creatinine increases were reported in 4 subjects (1.2%). Grade 3 or 4 lymphopenia was reported in 42 subjects (12.2%), and neutropenia in 15 subjects (4.4%).

Table 2. Laboratory Test Results Reported for Subjects with Solid Tumors Receiving Single-Agent AG 013736

Group/Parameter ^b	N	n (%) ^a at Maximum Grade				Total
		Grade 1	Grade 2	Grade 3	Grade 4	
Chemistry						
Total Bilirubin	347	44 (12.7)	21 (6.1)	2 (0.6)	2 (0.6)	69 (19.9)
Hypoalbuminemia	343	117 (34.1)	39 (11.4)	6 (1.7)	0 (0.0)	162 (47.2)
SGOT ^c	347	113 (32.6)	20 (5.8)	11 (3.2)	0 (0.0)	144 (41.5)
SGPT ^d	345	88 (25.5)	32 (9.3)	7 (2.0)	0 (0.0)	127 (36.8)
Alkaline Phosphatase	339	108 (31.9)	26 (7.7)	6 (1.8)	0 (0.0)	140 (41.3)
Creatinine	347	103 (29.7)	25 (7.2)	0 (0.0)	4 (1.2)	132 (38.0)
Hypernatremia	347	21 (6.1)	1 (0.3)	0 (0.0)	0 (0.0)	22 (6.3)
Hyponatremia	347	108 (31.1)	0 (0.0)	16 (4.6)	0 (0.0)	124 (35.7)
Hyperkalemia	347	74 (21.3)	24 (6.9)	9 (2.6)	0 (0.0)	107 (30.8)
Hypokalemia	347	46 (13.3)	0 (0.0)	4 (1.2)	0 (0.0)	50 (14.4)
Bicarbonate	261	67 (25.7)	9 (3.4)	1 (0.4)	1 (0.4)	78 (29.9)
Hypercalcemia	171	23 (13.5)	1 (0.6)	1 (0.6)	1 (0.6)	26 (15.2)
Hypocalcemia	171	29 (17.0)	11 (6.4)	1 (0.6)	2 (1.2)	43 (25.1)
Hyperglycemia	344	158 (45.9)	56 (16.3)	13 (3.8)	0 (0.0)	227 (66.0)
Hypoglycemia	344	47 (13.7)	10 (2.9)	2 (0.6)	1 (0.3)	60 (17.4)
Hematology						
Hemoglobin	347	134 (38.6)	30 (8.6)	0 (0.0)	3 (0.9)	167 (48.1)
Platelets	346	68 (19.7)	4 (1.2)	1 (0.3)	2 (0.6)	75 (21.7)
White Blood Cells	347	52 (15.0)	12 (3.5)	0 (0.0)	1 (0.3)	65 (18.7)
Neutrophils (Abs)	344	32 (9.3)	10 (2.9)	3 (0.9)	12 (3.5)	57 (16.6)

Lymphocytes (Abs)	345	65 (18.8)	60 (17.4)	29 (8.4)	13 (3.8)	167 (48.4)
-------------------	-----	-----------	-----------	----------	----------	------------

Urinalysis

Urine Protein	337	63 (18.7)	72 (21.4)	11 (3.3)	0 (0.0)	146 (43.3)
---------------	-----	-----------	-----------	----------	---------	------------

Data in table represents combined laboratory data from individual studies including Protocols A4061011, A4061012, A4061014, A4061015, A4061022, A4061023, A4061027, A4061035, and A4061044

^a Number of subjects at their maximum after-dosing grade

^b Only laboratory values which fall within CTCAE grading criteria are included

^c SGOT = Aspartate aminotransferase

^d SGPT = Alanine aminotransferase

For purposes of the informed consent, toxicities (all grades) noted to occur in > 35% of the study population in the aforementioned single-agent trials of axitinib are denoted “Most Common”. Toxicities (all grades) occurring in < 35% of the study population are denoted as “Less Common”.

Note: Axitinib in combination with other agents could cause an exacerbation of any adverse event currently known to be caused by the other agent, or the combination may result in events never previously associated with either agent

